    - o If the T-score is at or above 65 on the Children's Depression Inventory 2nd Edition Self-Report Short Version (CDI 2:SR[S]), an evaluation of depression by the Investigator (if qualified as a mental health professional) or by the Investigator in consultation with a mental health professional must be performed to exclude a clinically significant depression
  16. This criterion was removed during Amendment 2
  17. Other documented clinically significant condition (including unstable medical and/or psychiatric conditions, chronic disease other than narcolepsy with cataplexy, porphyria, or history or presence of another neurological disorder) that might affect the subject's safety and/or interfere with the conduct of the study in the opinion of the Investigator
  18. An electrocardiogram (ECG) with clinically significant deviation(s) from normal, or clinically significant physical examination findings, as determined by the Investigator
  19. Any clinically significant laboratory abnormality as determined by the Investigator
  20. A positive pregnancy test result at screening (pregnancy tests will be performed for any female subject who has reached menarche)
  21. A positive urine drug screen for benzodiazepines or drugs of abuse, a positive alcohol test, a history of substance abuse including alcohol abuse, or unwillingness to refrain from consuming alcohol during the study (if the subject takes prescribed amphetamines, a positive result for amphetamines will not exclude the subject)
  22. Treatment with benzodiazepines, non-benzodiazepine anxiolytics/hypnotics/sedatives, neuroleptics, opioids, barbiturates, diclofenac, valproate, phenytoin, ethosuximide within 2 weeks prior to enrollment (discontinuation for the purpose of study enrollment is permitted only if considered safe by the Investigator and approved by the Medical Monitor)
  23. Treatment with any other medications that have anticonvulsant effect (e.g., serotonin-norepinephrine reuptake inhibitors [SNRIs], selective serotonin reuptake inhibitors [SSRIs], or tricyclic antidepressants [TCAs]) within 1 month before Part 1 Screening
  24. Current treatment with oral isotretinoin
  25. Inability to fast for 2 hours before the first dose through 4 hours after the last dose of Xyrem on PSG and PK nights
  26. Lack of parental (or legal guardian) commitment to ensuring home situation is safe for Xyrem use, in the opinion of Investigator

Xyrem® (sodium oxybate) oral solution  

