## 5.7 Concomitant Therapy

In this study, the following medications are prohibited:

- Benzodiazepines, non-benzodiazepine anxiolytics/hypnotics/sedatives, neuroleptics, opioids, barbiturates, diclofenac, valproate, phenytoin, and ethosuximide are prohibited during the study and must have been discontinued within 2 weeks prior to the beginning of the Stable-Dose Period for subjects on Xyrem at study entry and the beginning of the Open-Label Titration Period for Xyrem-naïve subjects. (Discontinuation for the purpose of study enrollment is only permitted if considered safe by the Investigator and approved by the Medical Monitor.) If a subject undergoes short-term out-patient procedures during the study and requires opioids or benzodiazepine use, study drug may be held for one night while these drugs are given. If opioid or benzodiazepine use is required for multiple days, the subject should be discontinued from the study.
- Other antiepileptic therapies (e.g., SNRI, SSRI, or TCA) are prohibited during Part 1 and must have been discontinued within 1 month before Part 1 Screening. (Discontinuation for the purpose of study enrollment is only permitted if considered safe by the Investigator and approved by the Medical Monitor.)
- Oral isotretinoin (Accutane) is prohibited during the study.
- Investigational drugs other than study drug are prohibited during the study.

The following concomitant medications are permitted during the study with the following stipulations:

- Stimulant therapy may be continued, adjusted, or initiated during the study; however, prior to Amendment 4, stimulant use if any must be a stable dose throughout the Stable Dose and Double-Blind periods.
- Other antiepileptic therapies may be allowed in Part 2 of the study
- Vitamins in normal doses may be continued (herbal supplements are prohibited)
- Acetaminophen (paracetamol) for fever, headache, or other pain in accordance with the allowable dose limits by age for each country and not to exceed the limits below:
  - Subjects 7 to 11 years of age: no more than 325 mg every 4 to 6 hours, not to exceed 1625 mg in 24 hours

- Subjects 12 years of age and older: no more than 650 mg every 4 to 6 hours, not to exceed 3250 mg in 24 hours
- Ibuprofen for fever, headache, or other pain in accordance with the allowable dose limits by age for each country and not to exceed the limits below:
  - Subjects 7 to 11 years of age: no more than 100 mg every 6 to 8 hours, not to exceed 400 mg in 24 hours

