#### 6.9.1.2 Drug and Alcohol Screen

At Part 1 Screening (Visit 1), the beginning of the Part 1 Open-Label Titration Period for Xyrem-naïve subjects (Visit 1.1), the start of the Stable-Dose Period for subjects previously on Xyrem (Visit 2), the end of the Double-Blind Treatment Period (Visit 4), and during the Open-Label Safety Period at Visits 5, 7, 9, 12, and 15 ([Appendix 1](#) and [Appendix 2](#)), an alcohol test and a panel of urinary drug screens will be performed. During Part 2, an alcohol test and a panel of urinary drug screens will be performed at Part 2 Screening, at Visit 18 (for re-enrollers only), at every 6-month visit (Visits 24, 30, and 36), and at Part 2 Study Termination/Part 2 Early Termination (Visit 42) ([Appendix 22](#), [Appendix 23](#), and [Appendix 24](#)). The panel of urinary drug screens will test for the following prohibited substances. (A positive amphetamine result will not exclude a subject who is taking prescribed amphetamines.)

- Amphetamine (not prescribed)
- Barbiturates
- Benzodiazepines
- Cannabinoids
- Cocaine
- Opiates

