## 6.14 Removal of Subjects from the Study or Study Drug

All subjects are free to withdraw from participation in this study at any time, for any reason, and without prejudice. The Investigator must withdraw any subject from the study if the subject or subject's parent(s)/guardian(s) requests to stop participating in the study.

The Investigator, Jazz Pharmaceuticals or its designee may remove a subject from the study at any time and for any reason.

If any of the criteria below are met during the study, study drug administration must be stopped and the subject discontinued from the study.

- Suicide risk reported or assessed by C-SSRS
- Clinically significant depression independent of narcolepsy symptoms
  - If the T-score is  $\geq 65$  on CDI 2SR[S], an evaluation of depression by the Investigator (if qualified as a mental health professional) or by the Investigator in consultation with a mental health professional must be performed to exclude clinically significant depression
- Any PSG parameters that indicate, in the judgment of the Investigator, a risk to the subject's safe continued participation
- Subject becomes pregnant
- A positive urine drug screen for benzodiazepines or drugs of abuse (if the subject takes prescribed amphetamines, a positive result for amphetamines will not exclude the subject) or any suspicion by the investigator of abuse or diversion of study drug
- A positive alcohol test
- 3-fold or greater elevation above the upper limit of normal (ULN) of alanine aminotransferase (ALT) or aspartate aminotransferase (AST) accompanied by an elevation of serum total bilirubin greater than two times the ULN
- Liver enzyme (AST, ALT) value greater than or equal to 5 times the ULN
- Experiences an intolerable AE that is related to the study drug and/or procedure
- Develops any clinically significant worsening in narcolepsy symptoms during the Stable-Dose Period
- Develops a clinically significant laboratory or ECG abnormality that is related to the study drug and/or procedure
- Requires a medication that is prohibited by the protocol, with the exception of short-term opioid or benzodiazepine use (see [Section 5.7](#))
- Does not follow guidelines or procedures specified in the protocol

Xyrem® (sodium oxybate) oral solution  
Clinical Study Protocol: 13-005 Amendment 5

Jazz Pharmaceuticals

- 
- Is lost to follow-up
  - Does not continue to meet certain entry criteria or meets certain exclusion criteria during the course of the study

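### The urine-screen stop rule in Section 6.14 has no exception for the short-term procedural benzodiazepine use that Section 5.7 permits

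*Protocol*

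**What the plan says.** Section 6.14 opens its list of stopping criteria in mandatory terms: "If any of the criteria below are met during the study, study drug administration must be stopped and the subject discontinued from the study". Two bullets in that list matter here.

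- **Urine screen:** "A positive urine drug screen for benzodiazepines or drugs of abuse (if the subject takes prescribed amphetamines". The parenthesis goes on to excuse an amphetamine result in such a subject. The bullet also covers any suspicion of abuse or diversion of study drug.
- **Prohibited medication:** "Requires a medication that is prohibited by the protocol, with the exception of short-term opioid or benzodiazepine use", with a cross-reference to Section 5.7.

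Section 5.7 prohibits benzodiazepines and opioids but makes an allowance for short-term out-patient procedures. If the child "requires opioids or benzodiazepine use, study drug may be held for one night while these drugs are given". The limit is stated next: "If opioid or benzodiazepine use is required for multiple days, the subject should be discontinued from the study".

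Section 6.9.1.2 sets the schedule and contents of the urine panel, which includes benzodiazepines and opiates. Its only exception is this: "A positive amphetamine result will not exclude a subject who is taking prescribed amphetamines".

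**The concern.** The same clinical event is treated in opposite ways. Taking a benzodiazepine for a short procedure is allowed in 5.7 and is expressly not a reason to stop under the medication bullet of 6.14. If that dose is still detectable at the next scheduled screen, the urine-screen bullet requires the child to be stopped.

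At stake is the treatment of a child who did nothing contrary to the protocol. The child would lose study drug and go through the early-termination assessments (6.14.1, 7.4.3) and the safety follow-up visit (7.4.4). If Part 1 had not been completed, Part 2 would be closed as well, because Sections 3.1.1 and 3.1.8 and exclusion criterion 35 tie entry to completion of Part 1. A site that kept the child, following the evident purpose of 5.7, would be departing from a rule worded as a must.

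**Working it through.** No arithmetic applies, so the check sets the provisions side by side.

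| Provision | Trigger | Consequence | Exception written there |
|---|---|---|---|
| 5.7 | Opioid or benzodiazepine needed for a short-term out-patient procedure | Study drug may be held one night; discontinue only if use runs to multiple days | The provision is itself the exception |
| 6.14, medication bullet | A prohibited medicine is required | Mandatory stop | Short-term opioid or benzodiazepine use |
| 6.14, urine-screen bullet | Positive screen for benzodiazepines or drugs of abuse | Mandatory stop | Prescribed amphetamines only |
| 6.9.1.2 | Positive result on the panel | Describes the test | Prescribed amphetamines only |

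1. *Does the medication-bullet exception carry over?* No. The lead-in to 6.14 makes any one criterion sufficient. The exception is attached to a different bullet with a different trigger, and the urine-screen bullet has its own, narrower exception.

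2. *Can the situation arise on study?* Yes. Section 6.9.1.2 schedules on-treatment screens at Visit 4, at Visits 5, 7, 9 and 12, and in Part 2 at Visits 24, 30 and 36. For a child continuing directly into Part 2, Visit 15 also counts: Sections 3.1.8 and 7.5.1 make it the Part 2 entry visit, with a urine screen and dispensing of study drug.

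3. *Can a site avoid it by timing?* Often. Visits 5, 7, 9, 12 and 15 and the scheduled Part 2 visits have windows of ±7 days (Appendices 1.1, 2.2 and 22), so a screen can be brought forward before a planned procedure or put back after it. Visit 4 can only be put back, by up to 3 days (7.1.5, 7.2.5). Section 7 lets the medical monitor approve visits outside the window. Nothing in 5.7 tells the site to move the screen, however.

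4. *Does it touch the efficacy comparison?* No. After the Day 1 screen (Visit 1.1 or Visit 2), the next scheduled screen is Visit 4, at the end of the two-week Double-Blind Treatment Period. No scheduled screen falls inside the period from which the primary endpoint is taken.

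5. *How many children?* The documents give no detection window for the panel, no assay cut-off and no rate of procedures. No percentage or count can be derived.

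**The case against.** The best case for leaving the text alone is that it is not a strict contradiction. One rule turns on needing a medicine, the other on a test result. The sponsor's intention to keep these children appears in 5.7 and again in the same 6.14 list, and the urine-screen bullet goes on to abuse and diversion, which suggests that undisclosed use is its target. A sensible site would read the bullets together. All of that makes this a drafting omission rather than a flaw of design, but it does not give a site authority to add an exception to a mandatory criterion that already states its own.

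A second argument is safety. Xyrem is a CNS depressant, and a strict, objective stop on a benzodiazepine-positive screen is a defensible rule. It is not the rule this protocol chose, though: 5.7 already lets study drug resume after a one-night hold. The proposed sentence adds no exposure beyond that and keeps the multi-day and abuse or diversion stops.

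The argument that the situation will be uncommon stands, and it is why the point is minor.

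Some stronger readings are tempting but unsupported:

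- **Exclusion criterion 21 as a second route.** Another 6.14 bullet reads "Does not continue to meet certain entry criteria or meets certain exclusion criteria during the course of the study". It does not identify those criteria, and nothing says that 21 is among them.
- **Opiates on the same footing.** Opiates are on the 6.9.1.2 panel, but the 6.14 bullet names only benzodiazepines and drugs of abuse. The opiate case holds only if opiates are counted as drugs of abuse, and the protocol does not say which opioids the panel detects.
- **Screening occasions as a measure of risk.** The number of scheduled screens shows where the conflict could occur, not how often it would.

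**Conclusion.** Wrong as written, and minor. Taken literally, the urine-screen bullet of 6.14 discontinues a child for the detectable trace of a benzodiazepine that 5.7 and the medication bullet of 6.14 allow. For benzodiazepines this follows from the wording alone. For opiates it is conditional, as set out above.

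Its practical size depends on two things the protocol does not give: how long a procedural dose stays detectable on the panel, and how often such procedures fall close to a screen. It arises only when a positive result coincides with a screen that was not moved. The likely reach is a few children at most, but that is a judgement and not an estimate. A reader might infer that the randomised comparison or the type I error is affected. The screening schedule gives no support for that.

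**What to change.** Add to the urine-screen bullet of Section 6.14, and mirror in Section 6.9.1.2:

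> A positive benzodiazepine result (or opiate result, where opiates are treated as drugs of abuse) explained by short-term use permitted under Section 5.7 and documented with dates on the Concomitant Medications CRF does not by itself require discontinuation; multi-day use remains subject to Section 5.7, and any suspicion of abuse or diversion still requires discontinuation.

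Exclusion criterion 21 can stay as it is for eligibility.

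The cost is one sentence in two places. Section 6.13 already requires indication, total daily dose and dates for every concomitant medicine, so no new procedure or data item is needed. Section 11.7 requires a formal amendment with IRB/IEC approval for any change, so the sentence is best carried in the next amendment.

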#### 6.14.1 Handling of Early Terminations

If a subject terminates early from the study, either at his or her request or the subject's parent(s) or guardian(s), or at the Investigator's discretion, the Investigator will record the reason(s) for early termination on the relevant CRF page and notify the Sponsor immediately. The specific reason for the withdrawal should be carefully documented on the CRF. For instance, rather than stating "withdrew informed consent," the specific reason for withdrawing the informed consent should be stated. All subjects who terminate early from Part 1 should undergo all early termination assessments in [Section 7.4.3](#). All subjects who terminate early from Part 2 should undergo all study termination assessments in [Section 7.5.5](#). Subjects who terminate from Part 2 of the study because they have reached 18 years of age will be considered to have completed the study.

It is vital to obtain follow-up data on any subject who terminated because of an AE, abnormal laboratory test, or ECG finding. In any case, every effort must be made to undertake safety follow-up procedures.

#### 6.15 Sponsor's Termination of Study

Jazz Pharmaceuticals reserves the right to discontinue the study at any time for any reason. Such a termination must be implemented by the Investigator, if instructed to do so by Jazz Pharmaceuticals in a time frame that is compatible with the subject's well-being.

In the situation of a serious issue/event causing study termination, the sudden stop of medication may be warranted. In the event the study is terminated for an administrative reason, Jazz Pharmaceuticals will provide a reasonable period to allow subjects either to be discontinued safely, or to obtain replacement medication. "A reasonable period" is defined as no less than 2 weeks from the time of site notification of impending termination.

Xyrem® (sodium oxybate) oral solution  
Clinical Study Protocol: 13-005 Amendment 5

Jazz Pharmaceuticals

## 6.16 Appropriateness of Measurements

The primary efficacy endpoint (change in weekly number of cataplexy attacks) measure, the Cataplexy Frequency Diary, is similar to the measure used in a prior study to establish efficacy in adults. Cataplexy frequency data will be collected daily in a cataplexy frequency diary. Both the Cataplexy Frequency Diary and the ESS (CHAD) have been evaluated for their face and content validity in children with narcolepsy (Mapi Study JZ13770A). The CGIC has been used extensively in clinical trials.

The PK parameters selected to characterize the PK profile of sodium oxybate are the standardized parameters used to characterize the PK profiles of all drugs. The blood collections for sodium oxybate concentrations will occur at specified time points up to 8 hours after the first Xyrem dose.

The parameters selected to assess the safety of the study drug are appropriate since they are routinely used to assess the safety profile of drugs in clinical studies and pertinent to known risks of Xyrem. The C-SSRS, CDI 2:SR[S], and MASC-10 have been validated for use in the pediatric population.

## 7 STUDY ACTIVITIES

Study activities through the Double-Blind Treatment Period are presented by the following subject groups: subjects on Xyrem at study entry (Section 7.1) and Xyrem-naïve subjects (Section 7.2). PSG night activities are described in Section 7.3. Study activities for the Open-Label Safety Period for all subjects are described in Section 7.4. Study activities for Part 2 (Open-Label Continuation Period) are described in Section 7.5 for subjects continuing directly into Part 2 from Part 1 and in Section 7.6 for subjects re-enrolling in Part 2 after completing Part 1. Additional visits as required by local regulations may be conducted during the study.

The medical monitor may give permission for visits outside any particular visit window to accommodate necessary changes to complete a particular visit (e.g., travel issues, parental or family illness, etc.).

Subjects entering the Double-Blind Treatment Period after Amendment 4 becoming effective will receive open-label Xyrem treatment during this period. Subjects entering the Double-Blind Treatment Period before Amendment 4 becoming effective will continue to receive double-blind treatment during this period.

### 7.1 Subjects on Xyrem at Study Entry–Safety, Efficacy, and PK Evaluation

A Schedule of Events for subjects on Xyrem at study entry is in [Appendix 1](#).

#### 7.1.1 Part 1 Screening Visit (Days –30 to -1) Subjects on Xyrem at Study Entry (Visit 1)

After the subject has provided assent and a parent(s) or guardian(s) has signed an ICF in accordance with local IRB/IEC requirements, the subject may be screened for enrollment

Xyrem® (sodium oxybate) oral solution  
Clinical Study Protocol: 13-005 Amendment 5

Jazz Pharmaceuticals

into the study. All subjects will provide their written informed consent prior to the performance of any study-related procedures. The Screening Visit (Visit 1) starts when a subject is assigned a subject number via IVRS/IWRS. Screening will occur within 30 days before dosing. (If needed, additional screening time may be granted with permission of the Medical Monitor. However, if it has been more than 45 days since the Screening safety labs pertinent to eligibility were drawn, these labs may need to be repeated as instructed by the Medical Monitor.)

The following study evaluations will be performed:

- Obtain subject assent and ICF signed by parent(s) or guardian(s). If the subject will be participating in the PK evaluation, obtain additional documented assent and consent for the PK evaluation.
- Review the inclusion/exclusion criteria.
- Interview parent(s)/guardian(s) to determine if the home situation is safe for Xyrem use and storage, and assess if there is a risk of use or abuse by family members or others living in the home.
- Obtain demographic information and record contact information for the parent(s) or guardian(s).
- Obtain a medical history, including past (prior to any narcolepsy treatment) and current symptoms of narcolepsy ([Section 6.3](#)).
- Complete the Clinical Global Impression of severity (CGIs) for Historical Narcolepsy Overall Severity Prior to any Narcolepsy Treatment ([Appendix 15](#)) and CGIs for Historical Cataplexy Severity Prior to any Narcolepsy Treatment ([Appendix 16](#)).
- Complete the CGIs for narcolepsy overall (current condition) ([Appendix 17](#)) and for cataplexy severity (current condition) ([Appendix 18](#)).
- Record usual bedtime and awakening time.
- Record all prior medications, including OTC and health and dietary supplements taken during the 30 days before Screening, and also record any concomitant medications.
- Confirm the subject has been on a stable dose of Xyrem for the previous 2 months. Confirm the subject has been on a stable dose of stimulants, if applicable, for the previous 2 months. Record the subject's prescribed usual dose and regimen of Xyrem and stimulants if applicable.
- Perform a physical examination, including a brief neurological examination and a Tanner Stage Assessment ([Appendix 5](#)) but excluding a full genitourinary exam.
- Record height and weight in ordinary indoor clothes (without shoes).
- Administer the following and record results:
  - ESS (CHAD) ([Appendix 6](#))
  - Columbia-Suicide Severity Rating Scale (C-SSRS) ([Appendix 8](#));  
Baseline/Screening version for subjects  $\geq 12$  years of age and Children's  
Baseline/Screening version for subjects  $< 12$  years of age)

- 
- Children’s Depression Inventory 2nd Edition Self-Report Short Version ([Appendix 9](#))
  - Multi-dimensional Anxiety Scale for Children (MASC-10) ([Appendix 10](#))
  - Obtain vital signs (systolic and diastolic blood pressure, pulse/heart and respiratory rate, and body temperature) after the subject has been resting for at least 5 minutes.
  - Obtain pulse oximetry reading on room air while the subject is fully awake.
  - Obtain blood samples for the following:
    - Routine hematology, chemistry, and thyroid function (see [Table 2](#))
    - Serum pregnancy test (only for female subjects who have reached menarche)
    - For PK subjects only: coagulation (PT/INR and PTT)
    - HLA DQB1:0602 (if the subject has no previous HLA DQB1:0602 result available and no documented CSF hypocretin level  $\leq 110$  pg/mL)
    - For girls <8 years of age: estradiol, FSH, and LH
    - For boys <9 years of age: testosterone, FSH, and LH
  - Obtain urine samples for urinalysis.
  - Perform alcohol test and urine drug screens.
  - Obtain a 12-lead ECG.
  - Schedule Screening PSG
  - Subjects will continue dosing with their own supply of Xyrem during the Screening Period, with the exception of the Screening PSG Night when Xyrem will be provided.
  - Instruct subjects or parent(s)/guardian(s) on how to complete the Dosing Diaries (Study Drug Dosing Diary in [Appendix 12](#) and Stimulant Dosing Diary in [Appendix 13](#)).
  - The Investigator must thoroughly review results of all screening procedures and confirm all eligibility criteria prior to enrolling the subject in the study. The PSG must be completed and reviewed before the subject is enrolled (For the PSG, follow the procedures in Column 2 of [Table 6](#) for “Subjects on Xyrem at study entry.”)
  - Schedule next visit
- 7.1.2 Start of Stable-Dose Period, Subjects on Xyrem at Study Entry (Visit 2, Day 1)
- Review inclusion/exclusion criteria to determine the subject’s eligibility to continue participating in the study.
  - Record height and weight in ordinary indoor clothes (without shoes).
  - Obtain vital signs (systolic and diastolic blood pressure, pulse/heart and respiratory rate, and body temperature) after the subject has been resting for at least 5 minutes.
  - Perform alcohol test and urine drug screens.
  - Obtain urine sample for pregnancy test (only for female subjects who have reached menarche).
  - Complete the CGIs for narcolepsy overall (current condition) ([Appendix 17](#)) and for cataplexy severity (current condition) ([Appendix 18](#)).

- Administer the following:
  - ESS (CHAD) ([Appendix 6](#))
  - SF-10 ([Appendix 7](#))
  - C-SSRS ([Appendix 8](#); Since Last Visit version for subjects  $\geq 12$  years of age and Children's Since Last Visit version for subjects  $< 12$  years of age)
  - CDI 2:SR[S] ([Appendix 9](#))
  - MASC-10 ([Appendix 10](#))
- Instruct subject and parent(s)/guardian(s) on how to complete the School Attendance Diary ([Appendix 14](#)) if the subject is currently attending school.
- Instruct subjects or parent(s)/guardian(s) on how to complete the Cataplexy Frequency Diary ([Appendix 11](#)).
- Review the dosing diaries for compliance with dosing (Study Drug Dosing Diary in [Appendix 12](#) and Stimulant Dosing Diary in [Appendix 13](#)).
- Record all AEs that occur after assent was given and the ICF was signed on the AE CRF.
- Record all concomitant medications that were taken after assent was given and the ICF was signed on the concomitant medications CRF.
- Dispense study drug at the subject's current stable dose. (Access IVRS/IWRS.) Provide instructions for dose administration and, if flavored diluent is requested and available, the preparation of study drug with flavored diluent to subjects/parent(s)/guardian(s). See [Section 6.10](#).
- Schedule Visit 3 in the morning, and inform subjects/parent(s)/guardian(s) that subjects must be fasting for IGF-1, GH, and prolactin testing when they arrive at the visit.
- For subjects in the PK evaluation during the Stable-Dose Period, perform procedures for PK Night 1 and PK Night 2 in [Section 7.1.3](#).

